## 8 Safety evaluation

Safety assessments include adverse events, infections, bradycardia events, laboratory tests, vital signs, ECG, pulmonary function tests (PFTs), ophthalmic examinations, and dermatology assessment.

All safety data will be summarized on the safety set. Some safety data (AEs, vital signs, labs, PFTs, and ophthalmic evaluations) will also be summarized on the follow-up set.

Unless otherwise specified, safety assessments more than 45 days after the study drug discontinuation will not be included in the summaries on the safety set but will be considered in the summaries on the follow-up set. The 45 days rule should be applied as follows:

45 days after the last study drug dose date will be the cutoff for safety data to be included in the summaries.

Adverse events starting/ending before the first dose date will be excluded from the adverse event summaries i.e. only treatment emergent AEs will be summarized by treatment.

Details of the safety data summaries will be provided in the sections below. All safety data will also be presented in the listings.

## 8.1 Adverse events

## 8.1.1 Adverse event date imputation

To ensure that all reported AEs are summarized, a conservative approach will be taken to impute the AE date when a partial date is available. AE date imputation is based on a comparison of the partial AE start date to the treatment start date (Table 4-1).

- 1. If the AE start date year value is missing, the AE start date will be imputed as the treatment start date.
- 2. If the AE start date year value is less than the treatment start date year value, the AE must have started before treatment. The following imputation rules will apply.
  - a. If the AE month is missing, the AE start date will be imputed as the mid year date (01JulYYYY).
  - b. If the AE month is not missing, the AE start date will be imputed as the mid month date (15MONYYYY).
- 3. If the AE start date year value is greater than the treatment start date year value, the AE must have started after treatment. The following imputation rules will apply.
  - a. If the AE month is missing, the AE start date will be imputed as the year start date (01JanYYYY).
  - b. If the AE month is not missing, the AE start date will be imputed as the month start date (01MONYYYY).
- 4. If the AE start date year value is equal to the treatment start date year value, the month values will be compared as follows.
  - a. If the AE month is missing or the AE month is equal to the treatment start month, the AE start date will be imputed as the date one day after treatment start date.
  - b. If the AE month is less than the treatment start month, the AE start date will be imputed as the mid month date (15MONYYYY).
  - c. If the AE month is greater than the treatment start month, the AE start date will be imputed as the start month date (01MONYYYY).

**Table 4-1 AE date imputation** 

MON MISSING	MON < CFM	MON = CFM	MON > CFM
(F)=TRTSTD	(F)=TRTSTD	(F)=TRTSTD	(F)=TRTSTD
Uncertain	Uncertain	Uncertain	Uncertain
( D ) = 01JULYYYY	( C )= 15MONYYYY	(C)= 15MONYYYY	( C )= 15MONYYYY
Before Treatment Start	Before Treatment Start	Before Treatment Start	Before Treatment Start
(B)=	(C)= 15MONYYYY	(A)=	(A)=
TRTSTD+1		TRTSTD+1	01MONYYYY
Uncertain	Before Treatment Start	Uncertain	After Treatment Start
(E)=	(A)=	(A)=	(A)=
			0.41.401.000.004
01JANYYYY	01MONYYYY	01MONYYYY	01MONYYYY
O1JANYYYY  After Treatment Start	O1MONYYYY  After Treatment Start	O1MONYYYY  After Treatment Start	O1MONYYYY  After Treatment Start
After Treatment Start		After Treatment Start	After Treatment Start
After Treatment Start	After Treatment Start Partial indicates date pr	After Treatment Start	After Treatment Start
After Treatment Start  Before Treatment Start	After Treatment Start  Partial indicates date propertial indicates date at	After Treatment Start	After Treatment Start Date
After Treatment Start  Before Treatment Start  After Treatment Start	After Treatment Start  Partial indicates date propertial indicates date at	After Treatment Start	After Treatment Start Date
After Treatment Start Before Treatment Start After Treatment Start Uncertain	After Treatment Start  Partial indicates date propertial indicates date at Partial insufficient to de	After Treatment Start Director to Treatment Start Date termine relationship to Total Communication (01MONYYYY,TRTSTE	After Treatment Start Date E Treatment Start Date
After Treatment Start Before Treatment Start After Treatment Start Uncertain LEGEND:	After Treatment Start  Partial indicates date propertial indicates date at Partial insufficient to de	After Treatment Start Fior to Treatment Start Determine relationship to Tourish (01MONYYYY,TRTSTE TRTSTD+1	After Treatment Start Date E Treatment Start Date
After Treatment Start Before Treatment Start After Treatment Start Uncertain  LEGEND: (A)	After Treatment Start  Partial indicates date propertial indicates date at Partial insufficient to de	After Treatment Start Fior to Treatment Start Date Ster Treatment Start Date Stermine relationship to Technology  K(01MONYYYY,TRTSTE  TRTSTD+1  15MONYYYY	After Treatment Start Date E Treatment Start Date
After Treatment Start Before Treatment Start After Treatment Start Uncertain  LEGEND: (A) (B) (C) (D)	After Treatment Start  Partial indicates date propertial indicates date at Partial insufficient to de	After Treatment Start Drief to Treatment Start Date termine relationship to Tourist TRTSTD+1 15MONYYYY 01JULYYYY	After Treatment Start Date E Treatment Start Date
After Treatment Start Before Treatment Start After Treatment Start Uncertain  LEGEND: (A) (B) (C)	After Treatment Start  Partial indicates date propertial indicates date at Partial insufficient to de	After Treatment Start Fior to Treatment Start Date Ster Treatment Start Date Stermine relationship to Technology  K(01MONYYYY,TRTSTE  TRTSTD+1  15MONYYYY	After Treatment Start Date E Treatment Start Date

## 8.1.2 Adverse events

In this section, the term adverse event (AE) will refer to any entry on the adverse events CRFs. All AEs including infections will be coded using the MedDRA dictionary. The MedDRA version 20.0 or higher will be used depending when the study is completed.

Adverse events will be summarized by presenting, for each treatment group, the number and percentage of subjects having any AE by primary system organ class and preferred term. SAEs, death, drug-related AEs, the AEs leading to premature discontinuation of study drug, AEs requiring study-drug dose adjustment or interruption and AEs requiring additional therapy will be presented in a similar format as AEs. Notable events will include death, nonfatal SAEs (including infections), and AEs (including infections) leading to study drug discontinuation. AEs that fulfill the risk search terms (defined in the case retrieval sheet) with RMP risk will be summarized by risk name and lower level terms.

SAEs include death and non-fatal SAEs. All SAEs starting after the first dose date, including those starting more than 45 days after study drug discontinuation, will be included in the summaries on the safety set.

Additionally, occurrence rates of AEs, i.e. occurrence of AEs per 100 patient year by primary organ class and preferred term will be summarized. The occurrence rate of an event is calculated as the number (n) of all such events that patients experience divided by the patient years (Ny), where patient years are calculated as the sum of the number of days on study drug of all patients divided by 365.25. The occurrence of AEs per 100 patient years, which is calculated as n/Ny\*100, will be presented.

AE summaries on the follow-up set will be conducted for the following time periods defined by days relative to study drug discontinuation: days 1 to 45 after study drug discontinuation, day 46 or later after study drug discontinuation.

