In the post-marketing setting, isolated delayed onset events, including transient asystole and the 1 unexplained death, within 24 hours of the first dose, have occurred. These events have been confounded by concomitant medication and/or pre-existing diseases and the relationship to fingolimod is uncertain. It is recommended that fingolimod not be administered to patients with a history of cardiovascular or cerebrovascular disease or to those patients taking heartrate lowering medication.

Glatiramer acetate consists of the acetate salts of synthetic polypeptides, containing 4 naturally occurring amino acids: L-glutamic acid, L-alanine, L-tyrosine, and L-lysine. The mechanisms by which glatiramer acetate acts in patients with MS are not fully understood. However, it is thought to act by modifying immune processes believed to be responsible for the pathogenesis of MS. This hypothesis is supported by findings of studies that have been carried out to explore the pathogenesis of experimental allergic encephalomyelitis.

Evidence supporting the effectiveness of glatiramer acetate (20 mg/day) in decreasing the frequency of relapses in patients with RRMS comes from 2 placebo-controlled studies. In a single centre study in 50 patients randomized equally to glatiramer acetate or placebo, the

average number of relapses per patient over 24 months was reduced from 2.7 on placebo to 0.6 in the glatiramer acetate arm (Bornstein et al, 1987). In a larger placebo-controlled multicentre study in 251 patients a reduction of the 2-year relapse rate from 1.68 on placebo to 1.19 on glatiramer acetate was observed (Johnson et al, 2001). Results in both studies were supported by beneficial effects of glatiramer acetate on MRI markers of inflammatory disease activity and on other relapse-related endpoints, as compared to placebo.

In addition, 3 trials comparing high-dose IFN with glatiramer acetate were conducted. In the REGARD (Rebif® versus glatiramer acetate in patients with RRMS) open-label study in 764 patients equally randomized to the two treatment arms, there were no significant differences between groups treated with 44 μ g of subcutaneous (SC) IFN β -1a 3 times a week and 20 mg of SC glatiramer acetate daily after 96 weeks of treatment in the time of the first relapse, the annualized relapse rate (IFN β -1a 0.30; glatiramer acetate 0.29), or magnetic resonance imaging (MRI) outcomes (number and change in volume of T2 active lesions) (Mikol et al, 2008).

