#### 3.8.1 Study Day 1 and other study days

The first day of administration of randomized study medication (i.e., the first dose date of the study drug) is defined as Study Day 1 or Day 1.

All other study days will be labeled relative to Day 1. For event dates on or after Day 1, study day for an event date is calculated as (event date – first dose date +1), which could be Day 1, Day 2, Day 3, etc. For event dates before Day 1, study day for an event date is calculated as (event date – first dose date), which could be Day -1, Day -2, etc., referring to one day, two days, etc., before Day 1, respectively. Duration of an event will be calculated as (event end date – event start date + 1).

One month is defined as 30 days.

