## 8.8.3 Dose monitoring experience

The overall dose monitoring experience refers to the following information: whether subjects are discharged after 6 hours post-dose or extended monitoring is required after 6 hours post-dose, whether subjects are hospitalized, whether subjects are required monitoring on the next day, whether subjects have symptomatic and/or treated bradycardia, whether subjects discontinue the study drug permanently, whether SAE is reported, and whether subjects are discharged but returned to clinic.

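### The SAP's general adverse event rule and its SAE sentence set different lower bounds, and they disagree on Day 1

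*SAP*

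**What the plan says.** Four parts of the SAP bear on which serious events enter the safety-set tables.

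- **Day numbering (section 3.8.1).** "The first day of administration of randomized study medication (i.e., the first dose date of the study drug) is defined as Study Day 1". An event on the date of first dosing is therefore a Day 1 event.
- **General rule (section 8).** At the start of treatment, "Adverse events starting/ending before the first dose date will be excluded from the adverse event summaries". At the end, unless something else is specified, "safety assessments more than 45 days after the study drug discontinuation will not be included in the summaries on the safety set".
- **SAE sentence (section 8.1.2).** The safety-set summaries are to include "All SAEs starting after the first dose date, including those starting more than 45 days after study drug discontinuation". The sentence just before it counts deaths as SAEs.
- **Outputs (sections 8.1.2.1 and 8.1.3).** Deaths and SAEs are tabulated by system organ class and preferred term, SAEs are also tabulated by risk name, and SAE occurrences are counted. Two registry tables are described as on-treatment, with no start date given in that section.

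**The concern.** The SAE sentence does two things. It lifts the 45-day upper limit for serious events, and it also states a lower bound. That lower bound is not the one in section 8. An SAE that begins on Day 1 survives the general rule but is not covered by the SAE sentence. A programmer building the SAE tables would naturally start from the sentence written for SAEs. Coded as a strict inequality, it would place such an event in the AE table but not in the SAE table.

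Day 1 is the wrong day to leave unclear in this trial. Protocol section 5.5.5 has the first fingolimod dose given before noon with at least six hours of observation on site, so the minimum monitoring window falls on Day 1. Protocol section 1.1 mentions post-marketing events, "including transient asystole and the 1 unexplained death, within 24 hours of the first dose", and the rationale for Amendment 01 says that the report of that death led to a review of cardiac safety. Only patients on capsules have this monitoring, so any loss would probably be uneven between arms.

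**Working it through.** The plan states no figure on this point, so the check is to apply each date rule to the possible onsets. Write *s* for the SAE start date and *d* for the first dose date (Day 1). The general rule keeps an event if *s* ≥ *d*, up to 45 days after discontinuation. The SAE sentence, read literally, covers an event if *s* > *d*, with no upper limit.

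| SAE onset | General rule (SAP 8) | SAE sentence, literal (SAP 8.1.2) |
|---|---|---|
| Before Day 1 | out | not covered |
| Day 1, before dosing | in (the rule uses dates) | not covered |
| Day 1, after dosing | in | not covered |
| Day 2 to 45 days after discontinuation | in | covered |
| More than 45 days after discontinuation | out | covered |

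The last row is the difference the sentence was plainly meant to create. The Day 1 rows are a second difference for which the SAP gives no reason.

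**Could 'after' simply mean 'on or after' here?** The SAP spells out inclusive bounds in other places: for study days (3.8.1), for choosing the baseline record (3.8.2), for the last on-drug assessment (3.8.5) and for per-protocol relapses (4.2.1.3). So the word cannot safely be taken as shorthand.

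**Do the imputation rules settle it?** Only in part. Section 8.1.1 gives its aim: "To ensure that all reported AEs are summarized, a conservative approach will be taken to impute the AE date". Its first rule is: "If the AE start date year value is missing, the AE start date will be imputed as the treatment start date". That puts an event with a missing year on Day 1, which serves the aim only if Day 1 starts count. But rule 4a puts an event in the treatment-start year, with month missing or equal to the start month, one day after treatment start. Under the literal SAE sentence the results are then hard to defend:

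- SAE with a complete date equal to Day 1: not covered.
- SAE with missing year, imputed to Day 1: not covered.
- SAE in the month of first dose with the day missing, imputed to Day 2: covered.

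**Size.** The number lost would be the number of SAEs with onset on Day 1, and the documents do not give it. What can be given is the effect per patient. Using the final randomized numbers in SAP section 10 as denominators, each patient whose only SAE began on Day 1 would lower the arm's SAE incidence by:

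- fingolimod 0.5 mg: 1/352 = 0.28 percentage points
- fingolimod 0.25 mg: 1/370 = 0.27 percentage points
- glatiramer acetate: 1/342 = 0.29 percentage points

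**The case against.** The strongest reply is that the SAP contains no rule that removes Day 1 SAEs. The SAE sentence includes events and excludes none. It does not contain the word *only*, and its evident purpose is to lift the 45-day limit. The one exclusion at the start of treatment is in section 8 and leaves Day 1 events in. Section 8.1.2 treats every entry on the adverse event forms as an AE and presents SAEs in the same format, so SAEs fall under that general rule too. Protocol section 7.1 counts any event after the start of study drug. First-dose events also have their own report: section 8.8.3 lists "whether subjects discontinue the study drug permanently, whether SAE is reported" within the dose-monitoring experience, and section 8.8.4 summarizes that experience by treatment group alongside bradycardia and ECG findings. The registry tables are defined by on-treatment status and not by the SAE sentence.

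Most of this stands. A reader might infer that the plan counts only SAEs from Day 2 and discards the rest, and the text does not say so. What the reply does not remove is the mismatch itself. The dose-monitoring summary shows whether an SAE was reported. It does not replace the SAE, death and risk-term tables by preferred term or risk name. The on-treatment label is not given a start date where it is used, so it does not settle the bound either.

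**Conclusion.** The SAP gives two lower bounds for SAEs that disagree on Day 1. A literal implementation of the SAE sentence would leave Day 1 SAEs and deaths out of the safety-set SAE and death summaries. This is an inconsistency in wording with a possible effect on a safety count. It does not show that the plan omits first-dose events.

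Three stronger conclusions are tempting and are not supported.

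- **A number of lost patients.** No document gives a Day 1 SAE rate. Protocol section 1.1 reports second-degree AV block in under 0.5% of patients on 0.5 mg, but that is not restricted to serious events, and the conduction abnormalities are described as typically transient and without symptoms.
- **That nearly all first-dose cardiac SAEs would be lost.** The post-marketing events in Protocol section 1.1 are described as isolated and delayed, within 24 hours. Some such events would begin on the next calendar day, which the literal sentence covers.
- **That glatiramer acetate would lose nothing.** Its patients are also first dosed on Day 1. That the loss would fall mainly on fingolimod is a reasonable expectation from the first-dose effects and monitoring, but it is not a documented fact.

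The conclusion rests on one assumption: that the tables might be programmed from the SAE sentence without reference to section 8. If the programs already use an inclusive bound, only the text needs correcting.

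**What to change.** 1. In SAP section 8.1.2, change the SAE sentence to read: *All SAEs starting on or after the first dose date*, leaving the rest of it unchanged.
2. State that a Day 1 onset known to precede dosing is not treatment-emergent. SAEs are reported from consent (Protocol section 7.2) and the date rules cannot separate the two cases, so changing the wording to an inclusive bound would not by itself settle this.
3. Check that the SAE, death, risk-term, occurrence and registry tables all use this bound, and define on-treatment in section 8.1.2.1 accordingly.

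The cost is a few words in the SAP and a program check. No new data are needed, and the efficacy analyses are not affected.

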#### 3.6 Study medication

Duration of exposure to randomized study medication will be summarized on the safety set by presenting the number (and percentage) of subjects being exposed for a minimum duration of time as specified in Table 1-3 Duration in terms of number of days as shown in the second column will be used in the summary for the display of duration.

Duration of exposure is the number of days on study drug during the core study phase. The days when the subject does not take the study drug will be excluded. That is, duration of exposure will exclude periods of temporary interruption of study medication. Note: for the last dosing interval entered on the Dosage Administration Record CRF, if the dosing end date is partial date, impute the first day for missing day and January for missing month.

Summary statistics of duration of exposure to study medication will also be presented, which included mean, SD, minimum, maximum, etc.

For each treatment group, the patient-years, which will be calculated as (the sum of the number of days on study drug for all subjects in the group)/365.25, will also be presented.

Table 1-3 Definitions of time-intervals used to summarize exposure to study medication

Duration	Duration in terms of number of days
Any Exposure	≥1 day
≥1 week	≥7 days
≥2 weeks	≥14 days
≥1 month	≥30 days
≥2 months	≥60 days
≥3 months	≥90 days
≥6 months	≥180 days
≥9 months	≥270 days
≥12 months	≥360 days

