#### 3.8.5 Safety data cutoff and visit windows for summaries on follow-up set

For safety summaries on the safety set, only data which are within 45 days (5 times the half life of FTY720, 9 days) after the last dose of study drug will be considered.

For safety summaries on the follow-up set, all data (including assessments or events more than 45 days after the last dose of study drug) will be considered.

The visit windows below will be used in summaries on the follow-up set.

- 1) Last assessment on study drug
- 2) Day 1 to 45 after study drug discontinuation

- 3) Month 3 (day 46 to 135) after study drug discontinuation
- 4) Month 6 (day 136 to 270) after study drug discontinuation
- 5) Month 12 (day 271 to 540) after study drug discontinuation

For the visit window 1), last assessment on or before the last dose date will be used. For visit windows 2) to 5), assessments collected during the specified day intervals after the last dose date will be used.

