#### 8.1.3 Data summaries for AEs

Summaries on the safety set by treatment group include:

- Incidence of AEs by SOC and PT
- Incidence of AEs that fulfill the risk search terms with RMP risk by risk name and level terms
- Incidence of AEs by SOC and PT and severity
- Incidence of deaths by SOC and PT
- Incidence of SAE by SOC and PT
- Incidence of SAEs that fulfill the risk search terms with RMP risk by risk name and level terms
- Incidence of AEs leading to study drug discontinuation by SOC and PT
- Incidence of AEs requiring study-drug dose adjustment or interruption by SOC and PT
- Incidence of AEs requiring additional therapy by SOC and PT
- Incidence of most frequent (>=1% for any group) AEs by PT
- Incidence of AEs related to study drug by SOC and PT
- Occurrence of AEs per 100 patient-years by SOC and PT
- Occurrence of SAEs by SOC and PT
- Occurrence of NSAEs by SOC and PT

Summaries on the follow-up set by treatment group include:

• Incidence of AEs by SOC and PT (days 1 – 45 after study drug discontinuation, and more than 45 days after study drug discontinuation)

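### The AE rate per 100 patient-years counts events outside the on-drug time it is divided by, which can inflate non-serious AE rates by up to about 12–15% under constant risk

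*SAP*

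**What the plan says.** **Denominator.** SAP 8.1.2 says that "patient years are calculated as the sum of the number of days on study drug of all patients divided by 365.25". SAP 3.6 builds patient-years for the exposure table in the same way and adds that "duration of exposure will exclude periods of temporary interruption of study medication".

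**Numerator.** SAP 8.1.2 counts all events of the given type and sets no on-drug condition. SAP 8.1.3 lists "Occurrence of AEs per 100 patient-years by SOC and PT" among the safety-set summaries. For those, SAP 3.8.5 considers "only data which are within 45 days (5 times the half life of FTY720, 9 days) after the last dose of study drug", and SAP 8 repeats the same cutoff. SAP 8.1.2 then makes an exception for serious AEs after the first dose: "including those starting more than 45 days after study drug discontinuation, will be included in the summaries on the safety set".

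No section adds the 45 days to patient-years, restricts the numerator of the rate to on-drug events, or removes events that start during an interruption.

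**The concern.** A rate per patient-year has a meaning only if the events were at risk of being counted during the time in the denominator, and only then. Here events can enter the numerator from three kinds of time that add nothing to the denominator: the 45 days after the last dose, temporary interruptions and, for serious AEs, any later follow-up.

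That time will be observed. The Protocol (Table 6-1) plans a follow-up visit 12 weeks after the last dose with AE collection. Protocol 5.5.10 keeps patients who stop drug in the study, and Protocol 5.5.6 allows interruptions.

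Rates per 100 patient-years are read as absolute risks and set beside rates from other studies. An excess that differs by type of event cannot be corrected by the reader. It also grows when exposure is shorter, so an arm with more early stopping is inflated slightly more.

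**Working it through.** The documents state no AE rate, patient-years or mean exposure, so there is no figure to reproduce. The one related piece of arithmetic is correct: 5 half-lives × 9 days = 45 days.

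**Inputs**
- Full exposure: 12 months × 30 = 360 days (SAP 3.8.1: "One month is defined as 30 days").
- Tail: 45 days (SAP 3.8.5).
- Stopping: the documents give only a 15% drop-out assumption (SAP 10). It refers to leaving the study, not to stopping drug, and is used here as a stand-in.
- Assumed: 0–40% stop drug, at day 180 on average.

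Let T be mean on-drug days and ρ the event rate in the tail divided by the on-drug rate.

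**Comparison A: same events, denominator extended by the tail.** Excess = (T + 45)/T − 1 = 45/T.

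**Comparison B: on-drug events over on-drug time.** Excess = ρ × 45/T.

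| Share stopping | T (days) | A, or B with ρ = 1 | B, ρ = 0.5 | B, ρ = 0.25 |
|---|---|---|---|---|
| 0% | 360 | 12.5% | 6.2% | 3.1% |
| 15% | 0.85 × 360 + 0.15 × 180 = 333 | 13.5% | 6.8% | 3.4% |
| 30% | 306 | 14.7% | 7.4% | 3.7% |
| 40% | 288 | 15.6% | 7.8% | 3.9% |

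An excess of 15% corresponds to T = 45/0.15 = 300 days. With ρ = 0 (events confined to treatment), B gives no excess.

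**Illustration.** Take 342 glatiramer patients (SAP 10) with T = 333. On-drug time is 342 × 333/365.25 = 311.8 patient-years; with the tail it is 342 × 378/365.25 = 353.9. Twenty events, all on Day 1, give 6.41 per 100 patient-years under the SAP rule, 5.65 with the extended denominator, and 6.41 when only on-drug events are counted.

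**Departures from these conditions**
- If 15% of patients have no post-dose observation, at T = 333: 0.85 × 45/333 = 11.5%.
- If 2% or 5% of the 333 days are interrupted: 378/(333 × 0.98) − 1 = 15.8%; 378/(333 × 0.95) − 1 = 19.5%.
- If serious AEs are counted to the 12-week visit at a constant rate: 84/360 = 23% to 84/288 = 29%, and more if early stoppers are followed to Month 12.

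**Between arms**
- 15% v 30% stopping at day 180: (1 + 45/306)/(1 + 45/333) = 1.0105.
- 15% v 35% stopping at an assumed day 150 (T = 328.5 and 286.5): (1 + 45/286.5)/(1 + 45/328.5) = 1.018.

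**The case against.** A reader might infer that every AE rate is overstated by 12–15%. The documents do not support that. The range needs a mean exposure they do not give, a complete tail and, against the on-drug rate, a hazard that does not fall after stopping. The Protocol itself describes events tied to treatment time: transient bradycardia after the first dose (1.1), and macular edema mostly in the first 3–4 months (Appendix 4). For such events the on-drug rate is hardly overstated. The range does not cover serious AEs either, because they are uncapped. This part of the objection stands.

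A reader might also infer that the safety comparison between arms is materially biased. It is not. Assume 352 patients with 328.5 on-drug days, so 352 × 328.5/365.25 ≈ 317 patient-years. An event at 5 per 100 patient-years then yields about 16 events, with a standard error of about 25% for one rate (1/√16) and 35% for a ratio (√(2/16)). A shift of 1–2% would be invisible, and the SAP plans no test or interval for these rates. This stands too.

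The scope is narrow. Of the 14 safety-set AE summaries in SAP 8.1.3, one is per 100 patient-years, and AEs after stopping are also tabulated separately on the follow-up set.

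The interruption component rests on reading days on drug as SAP 3.6 does. Supportive analysis 3 in SAP 4.2.1.2 uses the same phrase for first-to-last-dose time. On that reading the interruption component disappears and the 45-day mismatch remains.

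Finally, the SAP document history says the rate wording was updated for consistency with study D2311. That explains the choice but does not align the windows. SAP 8.1.2.1 limits its registry tables to on-treatment events, whereas the rate definition carries no such limit.

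**Conclusion.** The mismatch is in the text and nothing elsewhere in the SAP resolves it. Followed as written, the rule gives a rate for no defined risk window.

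For non-serious AEs the inflation is up to about 12–15% relative to matched person-time. This assumes a constant hazard, complete 45-day follow-up and mean exposure of 300–360 days. Against the on-drug rate it runs from zero, for events confined to treatment, to about 15%. It may be higher with frequent interruptions, and for serious AEs if the uncapped ones enter this table. Between-arm distortion is about 1–2%.

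The percentage incidence tables and the efficacy analyses are not touched. The correction is worth making because it is small and the table reports absolute rates, not because any conclusion about the arms is likely to change.

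**What to change.** In SAP 8.1.2, state one window for this table and apply it to both numerator and denominator. Either of these would do:

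1. **Extended window.** Patient-years = sum over patients of [min(last dose date + 45 days, last contact date) − first dose date + 1]/365.25, interruptions included. Count only AEs that start in that window.
2. **On-drug window.** Keep patient-years as days on drug under SAP 3.6, and count only AEs that start on drug, so not during an interruption or after the last dose.

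The first keeps the SAP's own five-half-life window. It dilutes rates of events confined to treatment and includes time when patients who stopped may be on other care. The second avoids that but leaves out events in the washout period.

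Under either option, keep later serious AEs in the SAE incidence tables and listings, so that no safety information is lost, and keep on-drug patient-years in the exposure table.

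**Cost.** One sentence in the SAP and one derived variable or event flag. The rates become somewhat lower, apart from those of events confined to treatment under the second option. They also no longer follow the wording aligned with study D2311; showing the present definition alongside, labelled as such, would preserve that comparison.
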